3.5.2.3 Change in pain on NPRS compared to baseline

An 11-point NPRS is used to assess patient's level of pain. A patient is asked "What was your pain level at the ulcer location over the last 24 hours?" and selects a score between 0 and 10, with 0 meaning no pain and 10 meaning the worst pain.

Summary statistics for each visit time point and change from baseline for NPRS through 12 weeks, 6 months and 12 months post-treatment will be presented with 95% CI. NPRS

assessments from both the EDC and sDCT will be combined and slotted into windows found in section 3.1. If a patient has more than one assessment during a timepoint, the worst (highest) NPRS score will be used.

Additionally, NPRS assessments will be summarized using shift tables by each visit and worst value post baseline.

3.5.2.4 Change on EQ-5D-5L quality of life assessment compared to baseline at 12 weeks and 12 months post-treatment

The EQ-5D-5L is a self-administered questionnaire consisting of 5 questions pertaining to specific health dimensions (mobility, self-care, pain, usually activities and anxiety and depression), and health status rating scale (visual analogue scale [VAS]). Each dimension has 5 levels: no problems, slight problems, moderate problems, severe problems, and extreme problems. If a patient has died, the last EQ-5D-5L dimension assessment prior to death will be imputed as extreme problems (coded as 5).

The VAS records the respondent's self-rated health on a 20 cm vertical, visual analogue scale with endpoints labeled 'the best health you can imagine' (Score=100) and 'the worst health you can imagine' (Score = 0). This information can be used as a quantitative measure of health as judged by the individual respondents. If a patient has died, the last EQ-5D-5L VAS assessment prior to death will be imputed as 0.

Each one digit number expressing the level selected for each dimension can be combined into a 5-digit number describing the respondent's health state. For example, the number 11111 represents the respondent not having any problems in all five dimensions. These 5-digit numbers are health states which can be converted to an index value, where 1 represents full health and 0 is equivalent to death. A health state could be considered worse than death and the index values for those states will be less than 0. The index value will be calculated as:

$$\text{Index Health State} = 1 - (\text{Dimension 1 Estimate} + \text{Dimension 2 Estimate} + \text{Dimension 3 Estimate} + \text{Dimension 4 Estimate} + \text{Dimension 5 Estimate})$$

Each dimension estimated is based on the levels chosen for each dimension and can be found in appendix section 4.1.

Summary statistics for each visit time point and change from baseline for the index health state will be presented with 95% CI. There will be no imputation for missing values.

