### 10.1 Statistical Analysis

---

The statistical analysis plan (SAP) will be a separate document and will be updated as required, in association with any protocol amendments prior to database lock. The SAP will include detailed descriptions of statistical methodology.

Summary statistics for continuous variables will include number of patients, means, medians, standard deviations, standard errors, minima and maxima. For categorical variables, frequencies and percentages will be given; 95% CI will be calculated using the Clopper-Pearson (exact) method for binary proportions. For time to event variables, the number of patients, number of events, the median and 95% CI of the median, and quartiles will be provided by the Kaplan Meier (KM) method.

Missing data will not be imputed.

Baseline is defined as the last available measurement taken before the first treatment.

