1.3 Study endpoints

The primary endpoints of the study are:

- Rate of epithelial migration (mm/week) measured by wound perimeter on photograph
- Wound closure at 12 weeks (± 1 wk) post-treatment
- Time from initial treatment with Varithena® to wound closure

The secondary endpoints of the study are:

- Percent of wounds remaining closed at 3 months (± 1 wk) post-wound closure date, non-healed wounds are not included in percent calculation
- For healed wounds, rate of VLU recurrence (at same site)
- Change in pain on NPRS compared to baseline at 12 weeks (± 1 wk), 6 months (± 1 wk), 12 months (± 1 wk) post-treatment
- Change on Euroqol five dimension five level questionnaire (EQ-5D-5L) quality of life assessment compared to baseline at 12 weeks (± 1 wk) and 12 months (± 1 wk) post-treatment
- Change in Venous Clinical Severity Score (VCSS) from baseline to 12 week (± 1 wk) and 12 month (± 1 wk) follow-up
- Number of ulcer-free weeks defined as weeks from time of closure (complete epithelialization is recorded) to date of recurrence (at same site) or last contact if no recurrence (at study completion or withdrawal)

2 Changes to protocol analysis

The interim analyses were expanded to look at hospitalization and safety information. Please see section 3.8 for further details.

Additional exploratory analyses from the Wound Health Index (WHI) will not be conducted.

NPRS analyses will use data from both the sDCT and the electronic data capture (EDC). The analysis will be summarized by each week through 12 weeks, 6 months and 12 months post-treatment. Additionally, the categories by severity will not be summarized but rather the numerical scale will be summarized and presented in a shift table. Refer to section 3.5.2 for further details.

Sub-group analyses will not be performed. There is not enough data collected for the analyses to be meaningful.

3 Statistical methods and analysis

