3.3 Disposition, Demographics, Baseline

3.3.1 Disposition

Patient disposition will be summarized for all patients. The following categories will be summarized:

- Number of patients screened
- Number and percentage of patients in the efficacy population
- Number and percentage of bilateral patients (2 target wounds)
- Number and percentage of patients who discontinued
- Reasons for discontinuation
 - Withdrawn
 - Lost to follow-up
 - Death
 - Study discontinued by sponsor
 - Other
- Duration on study (months)
 - Duration (months) = (earlier date of study exit/death – date of first treatment + 1)/30.4375

Reasons for discontinuation and study exit dates are collected outside of the EDC. The reasons will be mapped into the categories above by clinical and provided to statistical programming for inclusion in summary table.

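### The SAP's death rule for EQ-5D-5L, as worded, replaces a patient's last observed answers with the worst state (index -0.573) and VAS 0; read instead as a fill after death, it scores death 0.573 below the SAP's own value of 0

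*SAP*

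**What the plan says.** Change in EQ-5D-5L from baseline at 12 weeks and 12 months is a secondary endpoint (Protocol 5.4, SAP 1.3). SAP 3.5.2.4 contains two rules for patients who die. For the five dimensions: "If a patient has died, the last EQ-5D-5L dimension assessment prior to death will be imputed as extreme problems (coded as 5"). For the rating scale: "If a patient has died, the last EQ-5D-5L VAS assessment prior to death will be imputed as 0".

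The same section describes the index as a scale "where 1 represents full health and 0 is equivalent to death" and allows negative values for health states judged worse than death. It closes with "There will be no imputation for missing values". Protocol 10.1 has the general rule "Missing data will not be imputed". The SAP section headed "2 Changes to protocol analysis" lists the departures from the protocol, and the death rule is not among them.

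SAP 4.1 gives the coefficient table and works one example, state 23245, to a printed index of 0.270.

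**The concern.** The two death sentences act on the last assessment before death. That is a completed form, not a missed one. Followed literally, they discard real data and still leave the visits after death empty. If the intention was to fill the visits missed through death, the sentences do not say so, and the value they give conflicts with the SAP's own anchor for death.

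The two readings produce different datasets, so two programmers working from this SAP could deliver different tables for a secondary endpoint. EQ-5D-5L is also summarised at the interim (SAP 3.8). A Week 12 answer reported there as observed could become the worst state in the final analysis if the patient later died. The replaced dimensions also feed the misery score in SAP 3.6, which would become 5 × 5 = 25.

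**Working it through.** **The SAP's own figure.** The index is 1 minus the sum of the five dimension estimates (SAP 3.5.2.4 and 4.1). For 23245 the printed terms match the table:

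- 0.096 + 0.107 + 0.068 + 0.318 + 0.321 = 0.910
- Index = 1 - 0.910 = 0.090, against 0.270 printed, an error of 0.180.

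The printed result does not reproduce. The formula and table are usable; only the result is wrong.

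**The state the death rule assigns.** The level 5 estimates in SAP 4.1 are 0.322, 0.261, 0.255, 0.414 and 0.321:

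- Sum = 1.573
- Index(55555) = 1 - 1.573 = -0.573.

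**Which value is overwritten under the literal reading.** Protocol Table 1 schedules EQ-5D-5L at Day 0, Week 12 and Month 12. Protocol 8.1.7 lists it under the Month 6 call but notes that it is collected only at 12 months. For a death before Month 12, the last form is therefore Week 12 if completed, otherwise baseline. Overwriting Week 12 changes the Week 12 change score; overwriting baseline changes only the baseline summary. The EQ-5D-5L row of the SAP 1.1.2 schedule shows four marks and may be broken in the text available. If a Month 6 form exists, that is the value overwritten.

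**Effect on the Week 12 mean of one death after a completed Week 12 form.** The observed value is assumed to be 0.50 to 0.90 for the index and 50 to 80 for the VAS. The 200 is the planned maximum. The 100 is an assumption, made because SAP section 2 drops the subgroup analyses with the remark "There is not enough data collected for the analyses to be meaningful".

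| Patients | Fall in mean index | Fall in mean VAS |
|---|---|---|
| 200 | (0.50 + 0.573)/200 = 0.0054 to (0.90 + 0.573)/200 = 0.0074 | 50/200 = 0.25 to 80/200 = 0.40 |
| 100 | 1.073/100 = 0.0107 to 1.473/100 = 0.0147 | 50/100 = 0.50 to 80/100 = 0.80 |

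**Effect on one patient.** Assume baseline 0.60 and Week 12 0.80. The true change is +0.20. Under the rule it is -0.573 - 0.60 = -1.173.

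**Effect on the confidence interval.** Take n change scores with assumed mean 0.10 and SD s, and replace one value of 0.20 by -1.173. The new sum of squares is (n - 1)s² - (0.20 - 0.10)² + (-1.173 - 0.10)² - n(1.373/n)². For s = 0.20:

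- n = 200: 7.960 - 0.010 + 1.621 - 0.009 = 9.561; new SD = √(9.561/199) = 0.219; ratio 1.096.
- n = 100: 3.960 - 0.010 + 1.621 - 0.019 = 5.552; new SD = √(5.552/99) = 0.237; ratio 1.184.

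The width of the interval grows in the same ratio:

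| Assumed SD | n = 200 | n = 100 |
|---|---|---|
| 0.15 | 1.165 | 1.309 |
| 0.20 | 1.096 | 1.184 |
| 0.25 | 1.062 | 1.121 |

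**Fill reading.** Each death lies 0 - (-0.573) = 0.573 below the SAP's death value. Per death this moves a visit mean by 0.573/200 = 0.0029 or 0.573/100 = 0.0057. An assumed 1 to 10 deaths among 100 patients would move it by 0.006 to 0.057. This conflict concerns the index only. A VAS of 0 is the bottom of its scale, and the misery score has no anchor for death.

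**The case against.** The strongest reply is that imputing normally means supplying a value that does not exist. On that view the sentences are a clumsily worded worst-value rule for death, and the fair complaint is ambiguity rather than destruction of data. The sponsor's intention is indeed unknown. But nothing in either document directs the rule to visits after death, and a programmer must work from the text.

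It can also be said that the SAP foresees negative index values, so -0.573 breaks no rule. The sentence allowing them concerns living health states, and death itself is placed at 0. A specific death rule may reasonably override the general no-imputation sentence in the same section. That does not settle the departure from Protocol 10.1 or its absence from SAP section 2.

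The points on size stand. No death count is given, the endpoint is secondary and descriptive, no hypothesis is tested, and the SAP's stated ground for stopping at the interim is safety. The -1.173 and the interval widening are illustrations under assumed values. The worked-example error is a separate slip and lends no support to the death-rule point.

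**Conclusion.** The concern holds. As worded, the rule replaces observed answers with an index of -0.573 and a VAS of 0. Under the alternative reading, it scores death 0.573 below the SAP's own anchor and makes an unlisted exception to the protocol. Neither reading fits the rest of the plan.

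The effect on a mean is small: roughly 0.003 to 0.015 index points per death across both readings, for 100 to 200 patients. The effect on an individual change score is large. One such value would widen the interval for the mean Week 12 change by about 10% with 200 patients or 18% with 100, at an assumed SD of 0.20. Over SDs from 0.25 down to 0.15, the ranges are 6% to 17% and 12% to 31%.

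The index values -0.573 and 0.090 follow from the SAP table alone. The effects on means and intervals rest on the assumed patient values, SDs and denominators. The 0.270 misprint alters results only if code is made to agree with it. This should be fixed, because the textual fault is certain and the remedy is cheap.

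**What to change.** 1. Delete the two death sentences from SAP 3.5.2.4, so that every completed EQ-5D-5L and VAS assessment is analysed as recorded.
2. Report the number of deaths by visit beside the EQ-5D-5L summaries, and state that later visits then describe survivors only.
3. If death is to be reflected in the scores, do it only at scheduled visits after death, as a labelled sensitivity analysis with index 0. State whether the VAS at those visits is 0 or missing. Leave the dimensions and misery score missing, since they have no level for death. List the analysis in SAP section 2 as an exception to the no-imputation statements in SAP 3.5.2.4 and Protocol 10.1.
4. Correct the 23245 example in SAP 4.1 to 0.090.

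The cost is two deleted sentences, one corrected number and one added row of counts. No visits or new data are needed. SAP 3.3.1 already tabulates death and uses the exit or death date, but notes: "Reasons for discontinuation and study exit dates are collected outside of the EDC". The counts by visit therefore need a merge from that source.

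A separate query, outside this point: confirm that the five-level form was used, because the sample page in Protocol Appendix G prints three options per dimension.

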3.5.2.5 Change in VCSS from Baseline to 12 week and 12 month follow-up

VCSS is a clinician rating of severity of chronic venous insufficiency ranging from 0 to 30, where higher scores indicate more severe venous disease. It assesses nine common signs/symptoms of venous disease: skin changes and pigmentation, inflammation and induration, and ulcers (including number, size, and duration). A tenth item assesses compression

compliance. Each item is scored individually on a 0-3 point scale. The revised VCSS clarifies ambiguities in category descriptions and contains an additional category for compression.

Summary statistics for each time point and change from baseline for VCSS total score at 12 weeks and 12 months post-treatment will be presented with 95% CI.

3.5.2.6 Number of ulcer free weeks (time to recurrence)

The number of ulcer free weeks (time between healed wound and recurrence) will be summarized by mean, median, standard deviation, quartiles, minimum and maximum. If a patient's wound healed but did not have a recurrence, the patient will be censored at the last date of study. Additionally, the distribution of the time to recurrence will be analyzed by KM methodology. The 25th percentile, median and the 75th percentile will be presented along with the 95% CIs using the methodology of Brookmeyer and Crowley (1982)² using the log-log standard error. KM rates will be presented for each week through 12 weeks with the corresponding 95% CIs using the log-log transformation methodology of Kalbfleisch and Prentice (1980)³. Plots of the KM curve will also be provided.

Information for recurrence will be based on data from the EDC.

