### 3. SCHEDULE OF REGISTRY ASSESSMENTS

Table 1

Registry Visit	Screening/ Baseline	Enrollment/ Treatment a (Day 0)	Week 1 Follow-Up Visit b	Week 2 through Wound Closure (at WCC) Weekly	Week 12 (±1wk) Follow-Up Visit	3 Months (±1wk) Post-Closure (phone call)	6 Month (±1wk) Follow-Up (phone call)	Month 12 (±1wk) Follow-Up Visit
Informed consent	X							
Duplex ultrasound of superficial and deep veins	X		X (as necessary)					
Screening: eligibility criteria	X							
Demographics, comorbidities, wound history	X							
Wound Characteristics		X c						
Varithena ® treatment		X (as necessary) d						
Hospitalizations for wound?		X	X		X	X	X	X
Subject training to use sDCT			X					
Review of VLU recurrence (if applicable)						X	X	X
Photograph(s) of wound (or closed wound area)	X	X c	X e	X e	X	X e,f	X e,f	X
Numeric Pain Rating Scale		X c	X e	X e	X	X e,f	X e,f	X
VCSS		X c			X			X
EQ-5D-5L quality of life assessment		X c			X			X

acompleted within 14 days of Screening/Baseline visit. Screening/Baseline and Enrollment/Treatment visit measurements and evaluations may occur at the same visit if subject is provided adequate time to consider and have all questions answered.

bnot required within first week; should be scheduled per SoC for first follow-up

cshould be completed prior to treatment with Varithena®

dadditional treatment with Varithena® cannot occur sooner than 5 days after index treatment

ecollected/completed by subject using sDCT

fInvestigator or designee to request during phone follow- up

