1.1 Study design

This 12 month, multicenter, open-label registry is designed to collect treatment and outcome data related to patients treated with Varithena® for great saphenous vein (GSV) system and/or anterior accessory saphenous vein (AASV) incompetence resulting in venous leg ulcer (VLU). Patients are treated per Investigator's standard of care (SoC) and in accordance with the full prescribing information (FPI) and instructions for use (IFU). For patients with healed ulcers during the 12 month follow-up period, VLU recurrence information is collected. Wound recurrence is defined as the reopening of a wound that was previously closed; all references throughout protocol to wound recurrence refers to wounds that are at the same location.

Note: In cases of cluster wounds, Investigator collects data for a single, primary wound. If more than one wound meets eligibility criteria, Investigator determines which wound to evaluate as the primary/target wound. All endpoint measurements are collected for the primary wound.

For each patient, participation in the registry lasts approximately 12 months. Patients are seen at the investigational site for initial treatment, about one week after treatment for initial follow-up visit (and retreatment if necessary), 12 weeks (± 1 wk) and 12 months (± 1 wk) after initial treatment. Between follow-up visits, and until wound closure, patients are asked to collect weekly photographs of the wound via the subject data capture tool (sDCT) during dressing changes at the wound care center (WCC).

Additionally, follow-up phone calls are placed at 3 months (± 1 wk) post-closure and 6 months (± 1 week) post-treatment. At that time, patients are asked to take a picture of the wound area and complete the numeric pain rating scale (NPRS) using the sDCT.

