3.4 Treatment and other medication and therapies

3.4.1 Study treatment

The following index treatment analyses will be summarized by target wound:

- Total injection sites
- Volume injected above the knee (mL)
- Volume injected below the knee (mL)

The number of patients with additional treatment will be summarized. Additionally, the number of additional treatments will also be summarized by wound along with the following:

- Leg (Right, left)
- For target wound? (Yes, no)

- Duration (days) from date of first treatment to the start of an additional treatment
 - $Duration\ (days) = date\ of\ additional\ Varithena\ treatment - date\ of\ first\ Varithena\ treatment + 1$
- Total injection sites
- Volume injected above the knee (mL)
- Volume injected below the knee (mL)

The number of additional treatments will be further split into the number of additional Varithena treatments and the number of adjunctive treatments. Adjunctive treatments are defined as the volume above the knee and below the knee are both 0 mL.

The following treatment analyses will be summarized by visit time point:

- Post-procedure duplex ultrasound performed (Yes, No)
- Duration between treatment and post-procedure duplex ultrasound
 - $Duration\ (days) = Date\ of\ post-procedure\ duplex\ ultrasound - date\ of\ first\ treatment + 1$
- Occlusion of target/treated vein? (Yes, No, N/A), for those that had a post-procedure duplex
- Compression compliance? (Yes, No)
- Hospitalized for target wound since last contact? (Yes, No)
- If wound previously closed/healed, was there recurrence? (Yes, No, N/A)
- Has previously healed target ulcer reopened? (Yes, No)

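### SAP 3.5.2.6 applies ordinary Kaplan-Meier to time to recurrence without defining the recurrence date, although recurrence is checked only at a few widely spaced contacts; if the contact date is used, early recurrence reads about half its true value or less.

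*SAP*

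**What the plan says.** SAP 1.3 defines ulcer-free weeks as running from closure "to date of recurrence (at same site) or last contact if no recurrence". SAP 3.5.2.6 adds three rules:

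- **Method:** "the distribution of the time to recurrence will be analyzed by KM methodology", with Brookmeyer-Crowley limits for the quartiles. A healed wound without recurrence is right-censored: "the patient will be censored at the last date of study".
- **Reporting:** "KM rates will be presented for each week through 12 weeks".
- **Source:** "Information for recurrence will be based on data from the EDC".

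The observation schedule is as follows.

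- **Until closure:** the subject photographs the wound about weekly at the wound care center (Protocol 8.1.4).
- **After closure:** SAP 1.1 says that "follow-up phone calls are placed at 3 months (± 1 wk) post-closure and 6 months (± 1 week) post-treatment". Protocol 8.1.6 to 8.1.8 list a recurrence assessment at those two calls and at the Month 12 visit.
- **Week 12:** the protocol schedule row "Review of VLU recurrence (if applicable") marks only those three contacts. The same row in SAP 1.1.2 carries one more mark, apparently at Week 12, but its columns cannot be read with certainty.

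SAP 3.4.1 lists the recurrence data by visit time point, for example "If wound previously closed/healed, was there recurrence? (Yes, No, N/A"), and a second Yes/No item on reopening. It lists no onset date. SAP 4.3, step 2, drops subject photographs taken after the closure date in the EDC. Interval censoring is mentioned in neither document.

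**The concern.** What the scheduled contacts establish is that a wound was closed at one contact and open at the next. That is an interval, not a date. Ordinary Kaplan-Meier needs a single date per event, and the SAP does not say which to use: the contact that found the recurrence, a date recalled by the subject, or a date from wound care records.

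The reporting grid sharpens the problem. The first call tied to closure comes about 13 weeks after it, yet the SAP tabulates the curve weekly for weeks 1 to 12. With contact dating, those rates depend largely on when a visit fixed to the treatment date happens to fall. Contact dating errs in one direction only: recurrences appear later and healing looks more durable. Ulcer-free weeks is a named secondary endpoint, and the recurrence rate is part of the registry objective. The printed confidence limits would not reflect the uncertainty about the dates.

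**Working it through.** The plan states no recurrence figure or event count, so there is none to reproduce. The check asks how large the shift would be if the contact date were used.

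**1. Gaps between contacts** (SAP 3.1 target days)

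- Month 6 to Month 12: 365 − 183 = 182 days = 26 weeks, or 28 at the ±1-week extremes.
- This gap applies to wounds closed by about week 13. For later closures the 3-month post-closure call falls after Month 6 and splits it. The longest gap is then about 23 weeks for closure at week 16, 19 weeks at week 20, and 13 weeks from week 26 on.

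**2. Which wounds can show a recurrence in weeks 1 to 12?**

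- Month 6 is week 183/7 = 26.1. It falls within 12 weeks of closure only for wounds closed after week 26.1 − 12 = 14.1.
- Month 12 is week 365/7 = 52.1. It does so only for closures after week 40.1.
- Without a Week 12 check, a wound closed before week 14.1 therefore has no scheduled recurrence check in its first 12 weeks. A Week 12 check helps only wounds already closed by then.

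**3. True cumulative recurrence under a constant hazard**

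The scenario rates are one-year recurrence figures in Protocol 4.1: 12% (surgery plus compression) and 28% (compression alone) in a randomised trial, and 7.1% in a radiofrequency ablation series. The weekly hazard is h = −ln(1 − p)/52.14, and F(t) = 1 − exp(−h·t).

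- 12%: h = 0.1278/52.14 = 0.00245, so F(12) = 2.9% and F(26) = 6.2%.
- 28%: h = 0.3285/52.14 = 0.00630, so F(12) = 7.3% and F(26) = 15.1%.

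**4. Contact-dated Kaplan-Meier**

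The simulation used exponential closure times (medians from about 8 to 20 weeks) and exponential recurrence. Each recurrence was dated at the next scheduled contact.

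| Rate per year | True, 12 weeks | With Week 12 check | Without it |
|---|---|---|---|
| 12% | 2.9-3.0% | 1.3-1.4% | 0.4-0.6% |
| 28% | 7.3% | 3.1-3.7% | 1.0-1.6% |

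The ratios are 1.4/2.9 = 0.48 and 3.7/7.3 = 0.51 with the check, so about half or less. Without it they are 0.6/2.9 = 0.21 and 1.6/7.3 = 0.22, so about a fifth or less. At 26 weeks and 28% per year, the curve reads about 11-12% against 15%.

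**5. Effect on ulcer-free weeks**

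- The mean delay among recurrences is 8.4 to 9.3 weeks; the maximum is 26.
- Over all healed wounds, the rise is the share recurring times the mean delay. With median closure at 12 weeks and a Week 12 check, it is 0.086 × 8.6 = 0.74 weeks at 12% per year (simulated means 36.31 and 37.06). At 28% it is 0.211 × 8.4 = 1.77 weeks (33.60 and 35.37).
- Across 7.1% to 28% per year the rise is about 0.4 to 2.1 weeks.

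**6. Does treating the data as intervals help?**

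An interval-censored exponential fit to the same contact data gave 7.3% against 7.3% true at 12 weeks, and 15.1-15.2% against 15.1% at 26 weeks (28% per year). That fit matches the simulated model, so it shows that the contacts carry the information. It does not show that a nonparametric estimator could place events within a gap. Mid-interval dating gave mean ulcer-free weeks among recurrers of 20.8-22.1, against 20.6-22.5 true and 29.5-31.6 with contact dating.

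**The case against.** The strongest reply is that the recurrence date may be a true onset date. The endpoint wording separates the date of recurrence from the last contact. The case report form on which the SAP is based is not in the documents, and SAP 3.4.1 lists summary items, not necessarily every field. With accurate onset dates the shift vanishes. This stands, and it makes the finding conditional. A reader might infer that ulcer-free weeks are in fact overstated; the documents do not show that. What remains is that the SAP leaves the date undefined and makes no allowance for error in a recalled one.

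Other limits also stand:

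- The phrase about events since the last contact in SAP 3.4.1 belongs to the hospitalization item. It is not evidence of how recurrence is asked.
- The 26-week gap is a maximum, not the typical gap.
- The 28% rate is from compression alone. The 12% and 7.1% rates come from patients whose veins were treated and are closer to this registry.
- The quartiles hardly move. In simulation the median is never reached. The 25th percentile is reached only at 28% per year, where it moves from about 45.5 to 46-48 weeks.
- A reader might infer that censoring at the last study date adds much unobserved ulcer-free time. SAP 1.3 ends follow-up at last contact, and both calls and the Month 12 visit include a recurrence assessment. The two dates should therefore coincide for most wounds. The point is minor and has not been sized.

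It can also be said that a descriptive registry with no hypotheses does not need an interval-censored main analysis. That is partly a matter of judgement, but weekly rates that mainly reflect the visit calendar do not describe recurrence well.

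**Conclusion.** The concern holds in conditional form. The SAP applies right-censored Kaplan-Meier, reported weekly through week 12, to an event scheduled to be assessed only at a few contacts, and it does not define the event date. If the contact date is used, recurrences are dated about 8 to 9 weeks late on average and the 12-week recurrence estimate is about half the true value or less. The effect on mean ulcer-free weeks over all healed wounds is small, about 0.4 to 2.1 weeks. The proportion recurred by Month 12 is unaffected, so a reading that the headline recurrence rate is biased is not supported.

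These sizes rest on exponential closure and recurrence times, detection only at scheduled contacts, and background rates that are not registry estimates. With true onset dates in the EDC the shift is zero; with partly accurate recall it would lie in between. This is worth correcting before analysis but does not undermine the registry.

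**What to change.** In SAP 3.5.2.6:

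1. State what the recurrence date is and where it comes from.
2. For each healed wound, derive from the EDC the last contact recorded closed and the first recorded open.
3. Estimate the recurrence distribution with an interval-censored (Turnbull) estimator, available in SAS as PROC ICLIFETEST. Keep Kaplan-Meier on recorded or mid-interval dates as a sensitivity analysis.
4. Report recurrence at the scheduled contacts instead of weekly through week 12.
5. Censor wounds without recurrence at the last recurrence check.

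Use EDC contact data only, because SAP 4.3, step 2, removes photographs taken after closure. State also whether Week 12 is a recurrence check, since the two schedules appear to differ.

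The cost is SAP wording, two derived dates per wound and one different procedure, with no new data. The drawback is wider intervals and a coarser curve, because the estimator cannot place events within a gap.
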